## 14 Data Handling and Record Keeping

### 14.1 Data Collection and Management Responsibilities

Data collection is the responsibility of the clinical trial staff at the site under the supervision of the site PI. The investigator is responsible for ensuring the accuracy, completeness, legibility, and timeliness of the data reported.

Data will be directly entered from the electronic medical record into electronic CRFs in the Institution-approved HIPAA Compliant and Encrypted version of REDCap. The original CRFs will be provided for use as source documents and maintained for recording if and when study visits occurred for each participant enrolled in the study.

Once all subjects have completed the study visits, Laboratory Evaluation windows will open up to +/-14 days of the target date to allow for the retrospective collection of data that accurately reflects the status of these subjects month-to-month as there is variability in the scheduling of labs due to many clinical factors. This will also more closely align with the window, +/- 28 days, for the bronchoscopies and DSAs that happen at these monthly visits as well.

The window for the Year 1 visits (Study Visit Week 52) will also open to +/- 30 days once all patients have completed the study for retrospective data collection. This enables Year 1 visits to properly capture data 1 year post-transplant and balances out the enrollment window given that the enrollment window for the trial is within 30 days post-transplant.

De-identified clinical data (including AEs, concomitant medications, and expected adverse reactions data) and clinical laboratory data will be assimilated in the study subject binders. Clinical data will be entered directly to electronic CRFs in REDCap.

### 14.2 Study Records Retention

Study documents will be retained for the longer of 3 years after close-out, 5 years after final reporting/publication, or 2 years after the investigation is discontinued. No records will be destroyed without the written consent of the sponsor, if applicable. It is the responsibility of the sponsor to inform the investigator when these documents no longer need to be retained.

### 14.3 Protocol Deviations

A protocol deviation is any noncompliance with the clinical trial protocol, GCP, or Manual of Procedures (MOP) requirements. The noncompliance may be either on the part of the participant, the investigator, or the study site staff. As a result of deviations, corrective actions are to be developed by the site and implemented promptly.

These practices are consistent with ICH E6:

- 4.5 Compliance with Protocol, sections 4.5.1, 4.5.2, and 4.5.3
- 5.1 Quality Assurance and Quality Control, section 5.1.1
- 5.20 Noncompliance, sections 5.20.1, and 5.20.2

It is the responsibility of the site PI/study staff to use continuous vigilance to identify and report deviations within 5 working days of identification of the protocol deviation, or within 3 working days of the scheduled protocol-required activity.

All protocol deviations must be addressed in study source documents, reported to the PI and Safety Monitor. During the course of routine follow-up, certain adjustments from routine clinical, laboratory, and bronchoscopy schedules are deemed necessary per the clinical judgement of the treating transplant

CONFIDENTIAL

This material is the property of the NYU School of Medicine and Langone Medical Center. Do not disclose or use except as authorized in writing by the study sponsor

pulmonologist. If study procedures or assessments are not performed based on clinical judgement, these routine adjustments shall not be deemed as protocol deviations or result in a report to the IRB.

Protocol deviations must be reported to the local IRB per their guidelines. The site PI/study staff is responsible for knowing and adhering to their IRB requirements. Further details about the handling of protocol deviations will be included in the MOP.

#### **14.4 Publication and Data Sharing Policy**

This study will comply with the NIH Public Access Policy, which ensures that the public has access to the published results of NIH funded research. It requires scientists to submit final peer-reviewed journal manuscripts that arise from NIH funds to the digital archive PubMed Central upon acceptance for publication.

The International Committee of Medical Journal Editors (ICMJE) member journals have adopted a clinical trials registration policy as a condition for publication. The ICMJE defines a clinical trial as any research project that prospectively assigns human subjects to intervention or concurrent comparison or control groups to study the cause-and-effect relationship between a medical intervention and a health outcome. Medical interventions include drugs, surgical procedures, devices, behavioral treatments, process-of-care changes, and the like. Health outcomes include any biomedical or health-related measures obtained in patients or participants, including pharmacokinetic measures and adverse events. The ICMJE policy, and the Section 801 of the Food and Drug Administration Amendments Act of 2007, requires that all clinical trials be registered in a public trials registry such as ClinicalTrials.gov, which is sponsored by the National Library of Medicine. Other biomedical journals are considering adopting similar policies. For interventional clinical trials performed under NIH IC grants and cooperative agreements, it is the grantee's responsibility to register the trial in an acceptable registry, so the research results may be considered for publication in ICMJE member journals. The ICMJE does not review specific studies to determine whether registration is necessary; instead, the committee recommends that researchers who have questions about the need to register err on the side of registration or consult the editorial office of the journal in which they wish to publish.

FDAAA mandates that a "responsible party" (i.e., the sponsor or designated principal investigator) register and report results of certain "applicable clinical trials":

- Trials of Drugs and Biologics: Controlled, clinical investigations, other than Phase I investigations of a product subject to FDA regulation;
- Trials of Devices: Controlled trials with health outcomes of a product subject to FDA regulation (other than small feasibility studies) and pediatric postmarket surveillance studies.
- NIH grantees must take specific steps to ensure compliance with NIH implementation of FDAAA.

### **15 Study Finances**

#### **15.1 Funding Source**

This study will be financed by an investigator-initiated study grant from the manufacturer of Envarus XR, Veloxis Pharmaceuticals, Inc.

#### **15.2 Costs to the Participant**

Participants will not incur any costs associated with participating in this trial.

### **16 Study Administration**

#### **16.1 Study Leadership**

The Principal Investigator will govern the conduct of the study. The PI, together with at least one coinvestigator will meet in person or by teleconference with the Safety Monitor at least quarterly

CONFIDENTIAL

This material is the property of the NYU School of Medicine and Langone Medical Center. Do not disclose or use except as authorized in writing by the study sponsor

and documentation of the meeting will be maintained.

## 17 Conflict of Interest Policy

The independence of this study from any actual or perceived influence, such as by the pharmaceutical industry, is critical. Therefore any actual conflict of interest of persons who have a role in the design, conduct, analysis, publication, or any aspect of this trial will be disclosed and managed. Furthermore, persons who have a perceived conflict of interest will be required to have such conflicts managed in a way that is appropriate to their participation in the trial. The study leadership in conjunction with the <specify NIH IC> has established policies and procedures for all study group members to disclose all conflicts of interest and will establish a mechanism for the management of all reported dualities of interest.

Any investigator who has a conflict of interest with this study (patent ownership, royalties, or financial gain greater than the minimum allowable by their institution, etc.) must have the conflict reviewed by the NYU Langone Conflict of Interest Management Unit (CIMU) with a Committee-sanctioned conflict management plan that has been reviewed and approved by the study sponsor prior to participation in this study. All NYULMC investigators will follow the applicable conflict of interest policies.

## 19 Attachments

These documents are relevant to the protocol, but they are not considered part of the protocol. They are stored and modified separately. As such, modifications to these documents do not require protocol amendments.

CONFIDENTIAL

This material is the property of the NYU School of Medicine and Langone Medical Center. Do not disclose or use except as authorized in writing by the study sponsor

## 20 Schedule of Events

Activity	Screening Visit (POD 0 to30)	SVD0*	SVW1 (+/- 5 days)	SVW2 (+/- 5 days)	SVW3 (+/- 5 days)	SVW4 (+/- 5 days)	SVW5 (+/- 5 days)
Study team procedures							
Consent	X						
Medical History	X						
Physical Exam	X						
Height	X						
Weight	X						
Vitals signs	X						
Review all recipient inclusion/exclusion criteria	X						
Study drug dispensation		X					
Participant study drug compliance check and accountability						X	
Bronchoscopy with biopsy						X	
Spirometry (FEV1)						X	
Donor-specific antibody						X	
Laboratory Evaluations							
Biochemistry			X	X	X	X	X
Hematology			X	X	X	X	X
Tacrolimus Co			X	X	X	X	X

SVD=study visit day; SVW=study visit week

\*Study visit day 0 = day of first drug dispensation and may occur on the same day as screening visit.

\*For SVW4 and SVW12: Bronchoscopies and DSAs will be done per SOC and as close to the specified study visit week as possible with a window of +/- 14 days.

CONFIDENTIAL

This material is the property of the NYU School of Medicine and Langone Medical Center. Do not disclose or use except as authorized in writing by the study sponsor

Activity	SVW6 (+/- 5 days)	SVW7 (+/- 5 days)	SVW8 (+/- 5 days)	SVW9 (+/- 5 days)	SVW10 (+/- 5 days)	SVW11 (+/- 5 days)	SVW12 (+/- 5 days)
Study team procedures							
Participant study drug compliance check and accountability			X				X
Bronchoscopy with biopsy							X
Spirometry (FEV1)			X				X
Donor-specific antibody							X
Laboratory Evaluations							
Biochemistry	X	X	X	X	X	X	X
Hematology	X	X	X	X	X	X	X
Tacrolimus C 0	X	X	X	X	X	X	X
Activity	SVW16 (+/- 5 days)	SVW20 (+/- 5 days)	SVW24 (+/- 5 days)	SVW28 (+/- 5 days)	SVW32 (+/- 5 days)	SVW36 (+/- 5 days)	SVW40 (+/- 5 days)
Study team procedures							
Participant study drug compliance check and accountability	X	X	X	X	X	X	X
Bronchoscopy with biopsy			X				
Spirometry (FEV1)	X	X	X	X	X	X	X
Donor-specific antibody			X			X	
Laboratory Evaluations							
Biochemistry	X	X	X	X	X	X	X
Hematology	X	X	X	X	X	X	X
Tacrolimus C 0	X	X	X	X	X	X	X

Activity	SVW44 (+/- 5 days)	SVW48 (+/- 5 days)	SVW52 (+/- 5 days)
Study team procedures			
Participant study drug compliance check and accountability	X	X	X

CONFIDENTIAL

This material is the property of the NYU School of Medicine and Langone Medical Center. Do not disclose or use except as authorized in writing by the study sponsor

Medical History			X
Physical Exam			X
Height			X
Weight			X
Vitals signs			X
Bronchoscopy with biopsy			X
Spirometry (FEV1)	X	X	X
Donor-specific antibody			X
Laboratory Evaluations			
Biochemistry	X	X	X
Hematology	X	X	X
Tacrolimus C 0	X	X	X

\*For SVW24, SVW36, and SVW52: Bronchoscopies and DSAs will be done per SOC and as close to the specified study visit week as possible with a window of +/- 28 days.

CONFIDENTIAL

This material is the property of the NYU School of Medicine and Langone Medical Center. Do not disclose or use except as authorized in writing by the study sponsor

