## 3 Objectives and Purpose

### 3.1 Primary Objective

The primary objective will be to assess the feasibility of early conversion to Envarsus XR at 1-year follow-up.

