### 4.2 Study Endpoints

#### 4.2.1

#### Primary Study Endpoints

The primary endpoint will be percentage of patients remaining on Envarsus XR at 1-year follow-up.

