### **10.4.2**

#### **Analysis of the Primary Efficacy Endpoint(s)**

The primary endpoint, percentage of patients remaining on Envarsus XR at 1-year, will be measured as a single endpoint on a nominal scale. It will be analyzed using descriptive statistics.

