### **10.4.4**

#### **Safety Analyses**

Safety endpoints include worsening chronic kidney disease and discontinuation of therapy will be analyzed as changes from baselines and summary data during the course of treatment, respectively. These will be compared as linear regression and frequencies using the chi-square test, respectively. All AEs will be ascertained and reported by the PI.

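### The 1-year percentage on Envarsus XR fits the stated objective, but the planned analysis discards when and why the drug was stopped and does not separate stopping from death on drug

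*Combined protocol and SAP*

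**What the plan says.** Section 3.1 sets the primary objective as to "assess the feasibility of early conversion to Envarsus XR at 1-year follow-up". Section 4.2.1 gives the matching endpoint: "The primary endpoint will be percentage of patients remaining on Envarsus XR at 1-year follow-up".

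Section 10.4.2 states that this endpoint "will be measured as a single endpoint on a nominal scale" and adds: "It will be analyzed using descriptive statistics". It gives no interval, no denominator and no rule for deaths or unknown status.

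Section 10.4.4 makes discontinuation of therapy a safety endpoint, reported as "summary data during the course of treatment" and compared as frequencies by chi-square. It mentions neither the timing of stops nor the reasons for them.

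Section 10.3 defines two sets: everyone who took one dose (safety), and only those completing the first post-transplant year (efficacy). It does not say which set the primary percentage uses.

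The Schedule of Events has a row "Participant study drug compliance check and accountability", marked at SVW4 and every 4 weeks to SVW52. Section 6.1.10 adds inpatient dose records and a medication review at each clinic visit.

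**The concern.** The pilot is about converting early, in hospital where possible. Section 2.1 explains why: outpatient conversion had produced subtherapeutic troughs, and daily inpatient monitoring might prevent that in the early post-transplant period. A programme where patients come off the drug within weeks of conversion is a different finding from one where they convert smoothly and a few stop late in the year. Both bear on 1-year feasibility, but they call for different next steps.

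The planned output gives the two the same number. The frequency in Section 10.4.4 does not help, because it is not tied to time or reason. The chi-square comparison adds little either: Section 5.1 requires historical controls to have completed a year on IR tacrolimus, so stopping the reference drug within that year is excluded by selection.

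Three kinds of patient are also left undefined in the percentage:

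- those who die while on drug;
- those who leave the study, whom Section 5.7.2 allows either to continue Envarsus XR or to return to IR tacrolimus;
- those switched under the safety review in Section 10.4.7.1 for reasons unrelated to their own tolerance.

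**Working it through.** The plan states no retention rate, target or power for this endpoint. Section 10.5 takes n = 40 from expected annual transplant volume and declines a power calculation, so there is no plan figure to reproduce. The stop counts below are assumptions.

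**1. Drug-status checks per patient (Schedule of Events).** SVW4 (1) + SVW8 and SVW12 (2) + SVW16 to SVW40 (7) + SVW44 to SVW52 (3) = 13. Equivalently, (52 − 4)/4 + 1 = 13.

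**2. Same primary result, different histories.** Take 40 dosed patients, 6 permanent stops, no deaths and no unknown status. The primary percentage is (40 − 6)/40 = 34/40 = 85%.

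The exact (Clopper-Pearson) 95% limits for x out of n are the 0.025 quantile of Beta(x, n − x + 1) and the 0.975 quantile of Beta(x + 1, n − x). For 34/40 they are 70.2% and 94.3%.

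With no deaths or censoring, the cumulative incidence of stopping at week t is (stops by week t)/40:

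| Pattern | Week 4 | Week 12 | Week 24 | Week 52 | On drug at 1 year |
|---|---|---|---|---|---|
| All 6 stop by week 4 | 6/40 = 15.0% (5.7 to 29.8%) | 15.0% | 15.0% | 15.0% | 85% |
| All 6 stop after week 40 | 0/40 = 0% (0 to 8.8%) | 0% | 0% | 15.0% | 85% |

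The primary result is identical in both rows; the week-4 figures are not.

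**3. Not special to 6 stops.** With 8 assumed stops, every pattern gives 32/40 = 80% at week 52 (64.4 to 90.9%). The number on drug at week 12 can be 32/40 (all stop by week 4), 38/40 (stops at weeks 4, 8, 16, 20, 28, 32, 40 and 48) or 40/40 (all stop at week 48). Mean time on drug, counting to week 52, is then:

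- all at week 4: (8 × 4 + 32 × 52)/40 = 42.4 weeks;
- spread over the year: (196 + 32 × 52)/40 = 46.5 weeks;
- all at week 48: (8 × 48 + 32 × 52)/40 = 51.2 weeks.

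**4. Denominator.** Suppose 34 of 40 dosed patients are on drug at 1 year, and k of the other 6 died or withdrew before completing the year. The completers-only set gives 34/(40 − k):

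- k = 0: 34/40 = 85%;
- k = 3: 34/37 = 91.9%;
- k = 6: 34/34 = 100%.

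The same experience could therefore be reported anywhere from 85% to 100%, depending on a set the plan does not name for this endpoint.

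**The case against.** The strongest reply is that objective and endpoint agree: both are set at 1-year follow-up. "Early" describes when conversion takes place (within the first month, Section 5.1), not when a failure counts. The Protocol Summary intends the drug to be maintained for the first year, so a stop in month 10 is a genuine retention failure. This stands. A reader might infer that the pilot cannot answer its own question; the documents do not support that, because the question as written is retention at 1 year and the endpoint measures it.

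A reader might also infer that the trial is unable to tell early from late stops. That too goes beyond the text. The four-weekly checks, inpatient dose records, clinic medication reviews and tablet reconciliation (Section 6.2) largely capture timing, and Section 10.4.2's wording does not forbid a display by visit. What is missing is a commitment to report it.

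Nor is it fair to say that 12 of 13 checks are wasted. Checks on one patient are strongly related; if stopping is permanent, being on drug at week 52 already implies being on drug at every earlier check. A ratio of used to scheduled checks does not measure lost information.

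Deaths are not hidden: 1-year survival is a secondary endpoint with a Kaplan-Meier analysis (Section 10.4.3). Only their place in the primary percentage is unstated. Finally, with 40 patients a competing-risk curve may add modestly to a dated listing. That is a reason to keep it descriptive; the listing alone would not settle the denominator or the handling of deaths and unknown status.

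**Conclusion.** The point holds as a gap in the analysis plan, not in the design or the data. The 1-year percentage is a suitable primary endpoint, but Sections 10.4.2 and 10.4.4 do not report when or why the drug was stopped and do not separate stopping from death on drug. In the illustration, 85% at 1 year is compatible with 15.0% or 0% having stopped by week 4. The unstated denominator could move the reported figure from 85% up to 100% if all 6 patients not on drug had also failed to complete the year.

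These sizes rest on assumed counts of stops, deaths and withdrawals in the planned 40 patients, since the documents give none. They also treat stops as permanent. The documents do not say that the completers-only set will be applied to the primary endpoint; the risk is that they leave it open. The early-week figures should not become the basis of the feasibility conclusion, because the plan sets no threshold for them and the objective is framed at 1 year.

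**What to change.** Keep the 1-year percentage as primary and revise Section 10.4.2 as follows.

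- **Primary figure.** Report the percentage remaining on Envarsus XR at 1 year with an exact 95% CI. The denominator is all patients who took at least one dose, not the completers-only set of Section 10.3. State how deaths on drug and unknown 1-year status are counted.
- **Supportive analysis.** Add: *Time from first dose to permanent discontinuation of Envarsus XR will be summarised as a cumulative incidence with 95% CI at weeks 4, 12, 24 and 52. Death on drug will be a competing event. Patients whose later drug status is unknown will be censored at the last known status.* Leaving the study while continuing the drug is not a stop. Timing from first dose matches the schedule, whose day 0 is first dispensation.
- **Listing.** List each stop by date and reason, from the compliance checks and the medical record. The first check is at SVW4, so earlier stops must be dated from the record.

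Label the last two as descriptive and supportive.

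The cost is one extra descriptive analysis and a few more reported figures beside the primary percentage. Stop date and reason would need adding to the case report form only if not already there; the form is not among the documents. No visit, procedure or patient is added.
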